10.0 Study Design / Methods

Multidisciplinary Team. We have assembled diverse talents to develop translational approaches to TMS treatment development for opiate dependence. Our team has extensive experience in: 1) TMS ([name]), 2) NIH trials in chronic lower back pain ([name], [name]), 3) pain management ([name]), 4) neuroimaging ([name]), and 5) statistical modeling ([name], [name]). In addition to providing critical effect size data for a planned R01, this grant will provide an opportunity for several MUSC trainees in the DART Resident research program ([name]), and a NIDA T32 ([name] [name]) to get hands-on training with neuroimaging, TMS, and opiate dependent individuals. [name] will serve as a scientific advisor and meet regularly with the team to provide insight on outcomes and patient recruitment.

Overview. The proposed study will be the first to employ a randomized, double-blind, sham-controlled design to parametrically evaluate the longitudinal effects of 16 days of rTMS to the DLPFC (Aim 1) or the MPFC (Aim 2) on self-reported pain and the brain's response to pain. This will be done in a cohort of patients recruited from MUSC clinics and the outer community with chronic lower back pain. Participants will be randomized to receive TMS to the DLPFC, MPFC, or sham (50% at each site), using a Latin square randomization. Resting state connectivity will be collected at each MRI scanning session.. Quantitative Pain Testing will be collected 12 times. MRI data will be collected 3 times: before the 1st visit of TMS, before the 12th visit of TMS, and before the 16th visit of TMS.

Table 1. Study Design. Aim 1&2 will be conducted in parallel.

^primary goal: evaluate 2 TMS strategies as tools to decrease acute pain and brain reactivity to pain.

^secondary goal: durability

Screening	Group Assignment	Induction Phase				Maintenance Phase				Follow Up Phase							
		Week 1	2	3	4	5	6	7	8	9	10	11	12	13	14	15	16
	TMS Sessions	XXX	XXX	XXX	XXX	X	X	X	X								
	Clinical Assessments	XXX	XXX	XXX	XXX	X	X	X	X	X	X	X	X	X	X	X	
	Quantitative Urinalysis	X	X	X	X	X	X	X	X	X	X	X	X	X	X	X	
	Quantitative Pain Testing	X	X	X	X	X	X	X	X	X	X	X	X	X	X	X	
	Neuroimaging				X				X								

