Participants. We will enroll 48 men and women 18-75 years old with CLBP that have a history of current prescription opioid use (>3 months) for the treatment of pain. Participants will be recruited through the community along with MUSC clinics. Patients that have previously agreed to be contacted for research and have current chronic pain will be referred to the study. Our prior history with targeted enrollment (See Significance) indicates this is feasible within 20 months, leading to full completion by 22 months. **Exclusion criteria:** Typical MRI and TMS exclusionary criteria, including metal above the neck or implanted in the body, use of prescription medications that lower seizure threshold, a history of seizures or traumatic brain injury, pregnancy or trying to become pregnant, current substance use or dependence (other than opioids and nicotine), history of seizure disorder, and claustrophobia. Participants will provide written informed consent following explanation of the study. **Sample size estimate:** A power estimate for Aim 1 and 2 was prepared using an original fMRI dataset previously collected in our laboratory (8). In this experiment, 18 healthy controls performed the same fMRI pain paradigm as the present study before and after a single session of 10 Hz rTMS. Mean parameter estimates for the “heat pain vs. rest” condition were extracted from several *a priori* regions of interest. These data yielded an effect size which ranged from 0.70 (thalamus) to 1.08 (insula) (n=15 yields 80% power using a two-sided p<0.05). Allowing for a 10% dropout rate after the screening visit, and up to a 20% dropout rate at the end of the Treatment phase (Week 4), as well as a 10% data loss rate for MRI (Aim 2) due to individuals with excessive head motion in the MRI scanner, screening 58 individuals should lead to complete data from 48 individuals (16 real DLPFC, 16 real MPFC, 16 sham (50% at each site)). Randomization will be handled by the MUSC data coordination center of the Biostatistical Unit ([name], biostatistician) and a Latin Square design with replacement will be used to ensure even enrollment across groups with replacement.

General Methods

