Screening Visit – Consent. Participants will receive a series of assessments designed to evaluate opioid dependence, psychiatric conditions, chronic pain and mood. These include the MINI International Neuropsychiatric Interview (46), Brief Pain Inventory (47), Timeline Followback (48), Becks Depression Inventory II (49), State-Trait Anxiety Inventory (50), the Pittsburgh Sleep Quality Index (PSQI), the Barratt Impulsiveness Scale (BIS), and Profile of Mood States (51). Data will be collected using REDCap™, and entered directly into the online portal to ensure security and prevent data loss.

Intervention –●MRI Visits 1-3. Following enrollment, participants will meet the study personnel for Assessment & MRI Scanning (details below). The procedures at MRI Visit 1 will be repeated at MRI Visit 2 (after 12 days of rTMS), and at MRI Visit 3 (after 16 days of rTMS). **●rTMS Treatment sessions:** After the Screening visit, patients will be randomized to receive 16 days of real or sham rTMS treatment. Based on prior studies in our laboratory that have applied 10 days of TMS to various clinical populations,

[figure not shown]

Figure 3. TMS stimulation sites, derived from EEG 10-20 landmarks.

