we expect 16 sessions of TMS treatments (3 days per week for 4 weeks, followed by 1 day a week for 4 weeks) will take 8 weeks, allotting time for a weekend (as is conventional in this field), holidays and/or one missed appointment. In the event that an individual drops out before completing the 16 TMS sessions, the number of sessions received will be a covariate in the analyses. Cortical Targeting: After the MRI scans participants will be escorted into the Brain Stimulation room (30 feet away) where scalp localization will be performed for the TMS procedure. The Cartesian position of the coil (X,Y,Z) will be determined by standardized positions from the EEG 10-20 system: 1) F3 (left DLPFC stimulation (Aim 1)), 2) FP1 (MPFC stimulation (Aim 2)). The angular position of the coil (pitch, yaw, roll) will be determined by the individual's cortical geography beneath FP1 and F3 using the individual's T1 scan for guidance. The locations and coil orientation will be indicated on a nylon cap which will be worn during the TMS sessions. We will then determine the participant's resting motor threshold (RMT, the minimal amount of stimulation required over the hand area of the primary motor cortex to induce contraction of the APB muscle of the hand 50% of the time) via the standardized PEST procedure (106, 107). During each TMS session, we will take a non-identifiable photo of the participants' forehead (eyes covered with an index card) to ensure the coil is correctly placed each time they return to the lab. This will be cross-checked with the neuronavigation data.

Strategy 1: iTBS to the left dlPFC. For intermittent theta burst stimulation (Aim 1), participants will receive 20 trains of stimulation over the dlPFC (middle frontal gyrus) (F3) (each train: 3 pulse bursts presented at 5Hz, 15 pulses/sec for 2 sec, 8 sec rest, 200 pulses/train; 110% RMT, MagPro; 600 pulses total) using a figure 8 coil (Coil Cool-B65 A/P).

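### The dropout allowance stops at Week 4, so the stated 48 with complete data (16 per arm) has no basis for MRI 3 at Week 8 or for follow-up to Week 15

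*Combined protocol and SAP*

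**What the plan says.** The sample size paragraph (Section 10.0, Participants) makes three allowances:

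- after screening: "Allowing for a 10% dropout rate after the screening visit";
- during treatment: "up to a 20% dropout rate at the end of the Treatment phase (Week 4";
- for imaging: "10% data loss rate for MRI (Aim 2) due to individuals with excessive head motion in the MRI scanner".

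It concludes that "screening 58 individuals should lead to complete data from 48 individuals", split as "16 real DLPFC, 16 real MPFC, 16 sham (50% at each site" participants.

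The schedule in the same section is longer than four weeks. The 16 TMS sessions are given as "3 days per week for 4 weeks, followed by 1 day a week for 4 weeks) will take 8 weeks". Table 1 labels Weeks 1-4 induction, Weeks 5-8 maintenance and Weeks 9-16 follow-up. It marks neuroimaging in Weeks 4 and 8 and the other assessments through Week 15; as the table reads, the Week 16 column is empty. The third scan is placed "at MRI Visit 3 (after 16 days of rTMS". The overview puts it just before session 16 instead, but either way it falls at about Week 8. Table 1 also names a "secondary goal: durability".

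**The concern.** On the plan's own schedule, Week 4 is the end of induction and halfway through the TMS course. The paragraph calls it the end of treatment, budgets no dropout beyond it, and then gives a complete-data figure with no time point attached. A reader would take 16 per arm to apply to all three scans and to follow-up.

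What is at stake is durability. Scan 3 is to be compared with scans 1 and 2 to see whether a reduction is sustained (Section 10.0, Neuroimaging Data). Section 2.0 lists a sustainable effect on pain as the first question to be answered. The trial is also meant to supply effect sizes for a larger study, so the number of people behind the later estimates, and hence their precision, matters. The only number the plan offers for them is one that its dropout allowance does not reach.

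**Working it through.** **Inputs.** All are from the sample size paragraph: 58 screened; losses of 10% (after screening), up to 20% (Week 4) and 10% (MRI head motion); 48 complete in three equal arms. The documents give no loss rate after Week 4. The 5%, 10% and 20% used below for Weeks 5-8 are assumptions; the largest equals the plan's own ceiling for the first four weeks.

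**Step 1: reproduce 58 to 48.** The figure implies an overall loss of 1 - 48/58 = 17.2%.

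- One 20% loss comes close: 48 x 1.2 = 57.6, although dividing gives 48/0.8 = 60 and 58 x 0.8 = 46.4.
- Two 10% losses come close: 58 x 0.9 x 0.9 = 47.0.
- All three in sequence do not: 58 x 0.9 x 0.8 x 0.9 = 37.6.
- All three added do not: 58 x (1 - 0.40) = 34.8.

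The 20% is a maximum. With no treatment-phase dropout at all, the two 10% losses still leave 47.0, just under 48.

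**Step 2: expected number at Week 4 under the stated rates.** For imaging, 37.6 / 3 = 12.5 per arm. For measures without the head-motion loss, 58 x 0.9 x 0.8 = 41.8, or 41.8 / 3 = 13.9 per arm. The latter is also the most that these rates leave for the non-imaging assessments at Week 15, reached only if nobody leaves after Week 4.

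**Step 3: carry the imaging number to MRI 3.** Expected n at Week 8 = 37.584 x (1 - L), where L is the assumed loss in Weeks 5-8.

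| Assumed L | Complete at Week 8 | Per arm |
|---|---|---|
| 5% | 35.7 | 11.9 |
| 10% | 33.8 | 11.3 |
| 20% | 30.1 | 10.0 |

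**Step 4: what 48 would require.** At Week 4, 48 / (0.9 x 0.8 x 0.9) = 74.1, so 75 screened. At Week 8, 48 / (0.648 x (1 - L)) gives 78, 83 or 93 screened for L = 5%, 10% or 20%.

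**The case against.** **The primary comparison is at Week 4.** The primary MRI comparison is visit 1 against visit 2. Table 1 calls durability secondary, and the Exploratory Aim and Exploratory Analysis hold the MRI durability comparison. Sizing on the primary time point is ordinary practice, especially in a pilot meant to derive effect sizes. This stands and limits the weight of the point. It does not rescue the complete-data figure, which the plan does not restrict to the first two scans.

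**Week 4 may be a slip.** Table 1 has no phase called treatment, and the 20% may have been meant for the whole TMS course. In that case 37.6 would be the Week 8 figure and only Weeks 9-15 would be uncovered. The text does not settle this, so the right request is to reconcile the two places.

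**Later dropout is foreseen.** The number of sessions received becomes a covariate for those who leave before session 16, and the randomisation is described as being with replacement. Neither supplies a loss rate. Replacement is unexplained and tied to even enrolment across groups, and Section 6.0 gives enrolment as 48.

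**A stronger reading to avoid.** A reader might infer a definite shortfall in power for the durability contrasts. The documents do not support one. The n=15 for 80% power is not identified as per arm or paired, and it comes from a before/after dataset. Fifteen is the smallest n reaching 80% in a two-sample test at an effect of 1.08, but also in a paired test at 0.78, inside the plan's range of 0.70 to 1.08. With 12 per arm and an effect of 1.08, power is 72% on the first reading and 93% on the second. Nor can the imaging effect be carried to the end of follow-up: Table 1 schedules no scan after Week 8, and the plan gives no effect size for sensory testing or questionnaires. Nor does the plan say that a non-significant scan 3 result would be read as loss of effect.

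**Conclusion.** The point holds in a limited form. The attrition basis of the sample size conflicts with the plan's own schedule, and 16 per arm cannot be claimed for MRI 3 or follow-up. At the stated rates and the assumed further losses, MRI 3 would have about 10 to 12 people per arm. This rests on three things: the losses apply in sequence, the 20% is taken at its ceiling, and it covers only the first four weeks. If it covers the whole TMS course, MRI 3 has about 12.5 per arm, still short of 16.

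The missing allowance after Week 4 does not touch the visit 1 to visit 2 comparison. It would be wrong to conclude that 48 is sound there, since the same rates do not produce it at Week 4.

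**What to change.** In Section 10.0, sample size paragraph:

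1. Reconcile the Week 4 label with Table 1 and the description of the TMS sessions, and say which period the 20% covers.
2. State the time point to which the complete-data figure refers.
3. Replace 48 with the number that the stated rates give at that time point. Restricting 48 to MRI visits 1 and 2 would keep a figure that the rates do not produce.
4. Give the expected n per arm for MRI 3 (Week 8) and for the last marked assessment (Week 15), under a stated loss assumption.
5. State that the n=15 and 80% power figure does not extend to the durability contrasts, and that these are reported as estimates with confidence intervals.

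This takes wording and a short recalculation, with no added participants or procedures. The price is a less favourable stated n, for durability and for the primary time point.

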An alternative strategy is to apply LTD-like stimulation to the medial prefrontal cortex (LTD-like mPFC rTMS (Strategy 2, Aim 2). This strategy is based on our understanding of functional neural architecture, wherein the SN is modulated by 2 other core networks: the executive control network (ECN) and the default mode network (DMN). As stated above, it is possible to attenuate activity in the SN through LTP-like TMS to the DLPFC, a node in the ECN. It is also possible to attenuate the SN through LTD-like TMS to the ventral medial prefrontal cortex (a node in the DMN). **The proposed study will be the first to employ a randomized, double-blind, sham-controlled design to parametrically evaluate the longitudinal effects of 16 days of rTMS to the DLPFC (Aim 1) or the MPFC (Aim 2) on self-reported pain and the brain's response to pain. This will be done in a cohort of patients recruited from the community as well as MUSC clinics with chronic lower back pain that have not been able to find adequate pain relief, whether or not they are using prescription opiates for 3 or more months.** Participants will be randomized to receive rTMS to the DLPFC (iTBS), MPFC (cTBS), or sham (50% at each site), using a Latin square randomization. Resting state connectivity will be collected 3 times: before the 1st day of TMS, after the 12th day of TMS, and before the 16th day of TMS (the last day administered).

Aim 1. Evaluate DLPFC rTMS as a tool to dampen pain and the engagement of the Pain Network. Hypothesis 1: DLPFC TMS will attenuate the baseline brain response to pain (Pain Network activity) and increase activity in the ECN when the patient is given instructions to ‘control’ the pain.

Aim 2. Evaluate MPFC rTMS as a tool to dampen pain and the engagement of the Pain Network. Hypothesis 1: MPFC TMS will also attenuate the baseline brain response to pain (Pain Network activity) but will not effect the ECN or SN when the patient is given instructions to ‘control’ the pain.

(Exploratory Aim): We will evaluate if there are rate-dependent effects between baseline SN connectivity with the ECN and DMN and the efficacy of each TMS strategy on subjective pain. Data will be analyzed by using multivariate pattern analysis (MVPA) (2014). While the primary outcomes will be MRI V1 vs V2, we will also examine the relative ‘durability’ of the effects on pain by comparing the MRI data at the end of all TMS visits between and within groups with factor analysis.

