5.0 Inclusion and Exclusion Criteria/ Study Population

Participants. We will enroll 48 men and women 18-75 years old with CLBP. These individuals can also have a history of current prescription opioid use (>3 months) for the treatment of pain. Participants will be recruited through MUSC clinics as well as the outer community. Patients that have previously agreed to be contacted for research will be referred to the study or contacted via telephone. The risks of MRI and TMS to the unborn fetus are not well understood. Therefore, to be included, females must not be pregnant

as determined by a urine pregnancy test and must be utilizing reliable birth control during the course of the study.

Inclusion Criteria:

1. Age 18-75 (to maximize participation)
2. Can currently be using prescription opiates
3. Able to read and understand questionnaires and informed consent.
4. Is not at elevated risk of seizure (i.e., does not have a history of seizures, is not currently prescribed medications known to lower seizure threshold)
5. Does not have metal objects in the head/neck.
6. Does not have a history of traumatic brain injury, including a head injury that resulted in hospitalization, loss of consciousness for more than 10 minutes, or having ever been informed that they have an epidural, subdural, or subarachnoid hemorrhage.
7. Does not have a history of claustrophobia leading to significant clinical anxiety symptoms.

Exclusion Criteria:

1. Any psychoactive illicit substance use (except marijuana and nicotine) within the last 30 days by self-report and urine drug screen.
2. Meets DSM-V criteria for current axis I disorders of obsessive-compulsive disorder, bipolar affective disorder, schizophrenia, dissociate disorders, eating disorders, and any other psychotic disorder or organic mental disorder.
3. Has current suicidal ideation or homicidal ideation.
4. Has the need for maintenance or acute treatment with any psychoactive medication including anti-seizure medications and medications for ADHD.
5. Females of childbearing potential who are pregnant (by urine HCG), nursing, or who are not using a reliable form of birth control.
6. Has current charges pending for a violent crime (not including DUI related offenses).
7. Does not have a stable living situation.
8. Suffers from chronic migraines.

Inclusion of Women and Minorities

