6.0 Number of Subjects

48 participants will be enrolled in this research study.

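### Screening 58 does not give 48 complete datasets under the plan's own loss allowances (about 38 at the stated maximum), and 48 enrolled conflicts with 48 complete

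*Combined protocol and SAP*

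**What the plan says.** The sample size paragraph in Section 10.0 lists three losses. The first two are dropout, the second of them counted to Week 4: "Allowing for a 10% dropout rate after the screening visit, and up to a 20% dropout rate at the end of the Treatment phase". The third is added to them: "a 10% data loss rate for MRI (Aim 2) due to individuals with excessive head motion". The sentence concludes that "screening 58 individuals should lead to complete data from 48 individuals", split 16 real DLPFC, 16 real MPFC and 16 sham. Just before this, the power statement is "n=15 yields 80% power using a two-sided p<0.05", for effect sizes from 0.70 (thalamus) to 1.08 (insula). It names no test and does not say whether 15 is per arm.

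The same paragraph ends by saying that "a Latin Square design with replacement will be used to ensure even enrollment across groups with replacement". No number of replacements and no rule are given.

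On enrolment, Section 5.0 says "We will enroll 48 men and women 18-75 years old with CLBP" and Section 6.0 says "48 participants will be enrolled in this research study". Section 10.0 also gives 48 as the number enrolled.

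Section 1.0 places the main imaging comparison between the first two scans: "While the primary outcomes will be MRI V1 vs V2".

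**The concern.** Going from 58 to 48 is a total loss of 17%. That is less than the 20% treatment-phase allowance alone, before the 10% after screening and the 10% of MRI data are taken off. The sentence therefore promises more complete datasets than its own allowances leave.

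The figure 48 also has two meanings. It is the number enrolled in three places and the number with complete data in the sample size sentence. Section 10.0 schedules the first scan after enrolment, so treatment dropout and MRI loss both fall after that point. The two meanings agree only if nobody is lost.

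At stake are the numbers to be screened, enrolled and analysed, which oversight and budgeting depend on. The plan says the trial's purpose is to supply effect sizes for a larger one, so the size of each arm with usable data decides how precise that product is.

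**Working it through.** **Inputs (all from the sample size paragraph in Section 10.0).** Screened 58; complete 48 (16 in each of three arms); loss after screening 10%; treatment dropout at most 20%; MRI data loss 10%. The plan does not say whether the 20% includes the first 10%, so each reading is tried.

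**Reproducing the plan's 58.** With all three allowances in use, no reading gives it. It does equal 48 × 1.20 = 57.6, rounded up. That would be a single 20% loss applied by multiplying by 1.20 instead of dividing by 0.80 (48 / 0.80 = 60). This origin is an inference; the plan does not show its calculation.

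**Yield of complete MRI data from 58 screened, and screening needed for 48.**

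| Reading | Yield from 58 | Per arm | Shortfall from 48 | Screened for 48 |
|---|---|---|---|---|
| 20% includes the first 10%, then MRI loss | 58 × 0.8 × 0.9 = 41.8 | 13.9 | 13.0% | 48 / 0.72 = 66.7, so 67 |
| Three losses in sequence | 58 × 0.9 × 0.8 × 0.9 = 37.6 | 12.5 | 21.7% | 48 / 0.648 = 74.1, so 75 |
| Losses added (40%) | 58 × 0.6 = 34.8 | 11.6 | 27.5% | 48 / 0.6 = 80 |

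**Treatment dropout below its ceiling.** In sequence, the yield is 58 × 0.9 × 0.9 × (1 − dropout) = 46.98 × (1 − dropout). For dropout of 0, 5, 10, 15 and 20% this is 47.0, 44.6, 42.3, 39.9 and 37.6. Keeping 45 (15 per arm) needs dropout of no more than 1 − 45/46.98 = 4.2%.

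**Chance of reaching 48.** If participants are lost independently, the binomial probability of at least 48 complete out of 58 is 0.2% at a retention of 0.648, 4.2% at 0.72, and 44% at 0.81 (no treatment dropout).

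**If 48 is the number enrolled.** MRI loss alone leaves 48 × 0.9 = 43.2 (14.4 per arm). Treatment dropout and MRI loss together leave 48 × 0.8 × 0.9 = 34.6 (11.5 per arm).

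**Effect on power and precision.** Power is from the noncentral t distribution, two-sided 0.05, with n taken per arm. Both tests are shown because the plan names neither.

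| n per arm | Two-sample, d = 0.70 | Two-sample, d = 1.08 | Paired, d = 0.70 | Paired, d = 1.08 |
|---|---|---|---|---|
| 16 | 48% | 84% | 74% | 98% |
| 13.9 | 43% | 78% | 68% | 96% |
| 12.5 | 39% | 73% | 62% | 94% |
| 11.6 | 36% | 70% | 58% | 92% |

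The stated 15 at 80% power fits a two-sample test at d = 1.08, which needs 14.5 per group, so 15. Confidence intervals widen by √(16/n): 7% at 13.9, 13% at 12.5 and 17% at 11.6.

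**The case against.** Five points can be made for the plan.

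- **The 20% is a ceiling.** This is true, so 38 is the yield at maximum losses and not a forecast. With no treatment dropout the yield is 47, one short of 48. But 48 is approached only by cancelling an allowance that the sentence says it has made.
- **MRI loss does not touch every outcome.** The assessments paragraph of Section 10.0 names quantitative sensory testing as the source of the primary dependent measures, and head motion does not affect those. Without MRI loss the yield is 58 × 0.9 × 0.8 = 41.8 (13.9 per arm), or 58 × 0.8 = 46.4 (15.5 per arm) if the 20% includes the first 10%. The second figure is above 15 per arm. If the two dropouts are sequential, 48 is reached when treatment dropout is about 8% or less (1 − 48/52.2). This stands as a limit on scope: the per-arm figures of 11.6 to 13.9 apply to MRI data. It does not save the sentence, which counts MRI loss towards complete data.
- **Dropouts may stay in some analyses.** Section 10.0 makes the number of sessions received a covariate for those who stop early. This helps the sensory testing and questionnaires more than a comparison that needs a second scan.
- **Dropouts may be replaced.** If they are, arm sizes and power need not fall. But more than 58 would have to be screened and more than 48 enrolled, so both stated figures would still be wrong. The power loss applies only where replacement does not make up the numbers.
- **It is a pilot, and much of the low power has another cause.** At d = 0.70 a two-sample test has only 48% power even with 16 per arm, and at d = 1.08 a paired test keeps at least 92% power throughout. Attrition is only part of the power problem. The arithmetic conflict does not depend on this.

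**Conclusion.** The concern holds. With all three allowances at their stated values, 58 screened gives about 38 complete MRI datasets (35 to 42 depending on how the losses combine), not 48: a shortfall of 13 to 28%. Each arm then has 11.6 to 13.9 participants instead of 16. That is below the plan's own 15, if 15 is read as per arm. The conflict between 48 enrolled and 48 complete is separate and also stands.

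The consequence for power and precision is more conditional. It assumes maximum losses, MRI outcomes and no replacement beyond the stated numbers. On those terms, going from 16 to 12.5 per arm costs about 9 to 11 percentage points of power for a two-sample test (48% to 39% at d = 0.70, 84% to 73% at d = 1.08), and confidence intervals are about 13% wider. The correction is necessary because the plan does not settle how many people are screened, enrolled and analysed.

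**What to change.** 1. State whether 48 means enrolled, randomised or complete, and make Sections 5.0, 6.0 and 10.0 agree.
2. If screening stays at 58, replace the yield sentence, for example:

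> At the planned maximum losses (10% after screening, 20% by Week 4, 10% of MRI data, applied in sequence), 58 people screened are projected to yield about 38 with complete MRI data (12–13 per arm; 35–42 depending on how the losses combine).

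If enrolment is capped at 48, use about 35 (11.5 per arm) instead.

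3. If 48 complete is the figure that governs, restate the screening number: 67 if the 20% includes the first 10%, 75 in sequence, 80 if the losses are added. Say which reading is meant.
4. Name the test behind the 15, say whether it is per arm, and give the power or confidence interval width at the projected number. Give the non-MRI yield separately.
5. Say how many replacements are allowed and whether they are screened in addition to the 58.

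Restating the yield costs wording and one recalculated number, and the stated completer count becomes less favourable. Keeping 48 complete means screening 9 to 22 more people. That may strain the 20-month enrolment estimate, although the plan gives no screening rate from which to judge this. Restating the yield changes no study procedure.
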